LICBT is a disorder-specific intervention, it adopts different CBT intervention strategies for different presenting problems, for example, behavioural activation for depression, worry time and problem solving for generalised anxiety, and exposure and habituation for panic and phobia. Transdiagnostic intervention has been gaining evidence over the past decade to target the underlying psychological mechanism and thus treat different presenting problems with the same set of strategies. Acceptance and commitment therapy (ACT) is one of the well-researched intervention approaches. Meta-analysis showed that ACT can effectively reduce the level of depression and anxiety, while brief ACT approach also showed promising results (Bai, Luo, Zhang, Wu, & Chi, 2020; Haller, Breilmann, Schröter, Dobos, & Cramer, 2021; Kyllönen, Muotka, Puolakanaho, Astikainen, Keinonen, & Lappalainen, 2018).

Mental Health in Hong Kong

Due to the huge success of the IAPT programme, its concept is worth borrowing and applying to Hong Kong. Mind Mental Health Hong Kong (Mind HK) has launched a programme named Improving Access to Community Therapies, or ‘iACT’ for short. iACT was developed in accordance with the IAPT programme and incorporated the principles of low-intensity psychological intervention and ACT principles. In this programme, Mind HK will train 30 bachelor’s degree holders to study a low-intensity psychological intervention programme. The study programme consists of 120 hours of intensive training and a 9-month placement in community settings, including non-government organisations, schools, and private clinics. The trained psychological well-being practitioners (PWPs) will provide low-intensity acceptance and commitment therapy (LIACT) to around 300 adults who are screened with mild to severe depressive or anxiety symptoms without imminent risk.

Individuals will later receive LIACT offered by PWPs and complete guided self-help workbooks with guidance. PWPs will be trained and supervised for providing LIACT. In addition to the 120-hour training, they received regular supervision from recognised supervisors, including clinical psychologists, social workers, and experienced counsellors. Aspects of case management and clinical skills will be covered during supervision. Despite the promising results of the IAPT programme, the effectiveness of LIACT in a local context has yet been examined.

Aims of the study

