The current study aims to conduct a comprehensive evaluation of a training curriculum designed for teaching low-intensity psychological interventions to bachelor's degree holders, specifically focusing on principles of Acceptance and Commitment Therapy (ACT) and its intervention effectiveness. This evaluation is divided into two integral parts. In the first part, the curriculum, which encompasses a 120-hour intensive teaching block followed by a nine-month placement, will be evaluated. To assess the trainees' competencies in applying the principles of ACT, a series of role-play examinations will be administered at various time points, including pre-training, pre-placement, mid-placement, and end-of-placement. Focus groups will be conducted.

The second part of the evaluation is to examine the outcomes of low-intensity psychological interventions, delivered by the trainees, targeting adult individuals (age ≥ 18) screened with mild to severe symptoms of depression and anxiety. To achieve this, a series of questionnaires will be administered at several stages: pre-intervention, during each session, and at a three-month follow-up. Outcome measures will include the assessment of depressive

and anxiety symptom severity, quality of life, functional impairment, therapeutic alliance, and the level of experiential avoidance. Individual exit interviews and focus groups will be conducted.

Hypotheses

It is hypothesised that the competency level of the training participants will increase after the intensive training block and the placement. It is hypothesised that after receiving the low-intensity psychological intervention based on the Acceptance and Commitment Therapy (ACT) principle, the depression and anxiety scores, functioning impairment, and experiential avoidance level will reduce, and quality of life and therapeutic relationship will improve.

Methodology

Training Participants

Participants from the Psychological Wellbeing Practitioners (PWPs) Programme will be invited to participate in the research. The PWPs are degree holders who will undergo 120 hours of intensive training block, followed by 9 months of placement to practise the learnt skills. Given therapist competency will be part of the programme, this research will request the participants to consent to the use of the data collected in the programme.

Service Participants

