Individuals with depression or anxiety symptoms will be sampled in this study. Participants will be recruited from the placement organisations and promotions on social media, web pages, and at mental health centres. The sample size is estimated to be 300 individuals for initial screening for LIACT-guided self-help services.

Inclusion criteria

1. Adults aged 18-65
2. Adults with a specific set of presenting problems
3. Anxiety problems (including social, generalised, health anxiety, work anxiety)
4. Mild to moderate depression
5. Other emotional challenges include (but not limited to): Low self-esteem, perfectionism, mild anger issues, interpersonal or relational challenges, low motivation, lack of purpose, and numbness

Exclusion criteria

1. Adults with the following features/presentations are not eligible for the PWP programme and should automatically lead to an onward referral:
2. High severity on depressive score (PHQ9 \geq 20)

3. High or imminent risk (according to scores on PHQ9 question no. 9 and information emerging at triage assessment, including indication of plan and action or the lack of protective factor)
4. Any of the following presentations or situations: diagnosis or features of a mental health problem that is not suitable for low-intensity intervention, obsessive compulsive disorder, post-traumatic stress disorder, bipolar disorder, schizophrenia and other psychotic disorders, dissociative disorders, personality disorders, eating disorders, gender dysphoria, paraphilic disorders, anger issues as primary presenting concern (without anxiety or depression), sleep issues as primary presenting concern (without anxiety or depression), psychotic experiences (e.g. hallucinations), substance-related disorders, history of trauma or abuse that is considered highly relevant to the current presenting problem they are seeking support for, planned changes to psychotropic medication during the period of PWP intervention, currently receiving regular psychological counselling or support from another practitioner for at least twice a month, diagnosis of a learning disability, cognitive impairment or neurodevelopmental condition that would impair their ability to engage with a structured, manualised intervention (e.g. untreated ADHD or moderate-severe brain injury), clear safeguarding concerns requiring multi-agency support (e.g. concerns about domestic abuse)

Research design

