For training evaluation, given the current training programme has already consists of therapist competency assessment to ensure the quality of the training participants. A record of role-play videos will be rated the ACT therapist competency by trained psychologists at pre-training, after intensive training block, mid-placement and post-placement. A consent form will be sent to the training participant to authorise the use of data for analysis. Repeated measures design will be adopted for this study.

Repeated measures design will be adopted for this study. Individual guided self-help LIACT service, eligible participants will receive 6-8 sessions of guided self-help LIACT over three to four months. Clinical outcomes (depression and anxiety levels) will be measured at every session, it will take around 5 minutes to complete these two routine outcome measures. Other primary and secondary outcome measures, including general well-being, functioning and activity impairment, psychological flexibility, experiential avoidance, and therapeutic alliance will be at 3 time points, namely pre-treatment, post-treatment (at the end of the last session) and 6-week follow-up. Participants will take around 20 minutes to complete the full package of assessments. These outcome variables will be additionally measured after each

session to avoid missing data if participants drop out. Recovery rate and reliable improvement rate will also be used as indicators to evaluate the efficacy of LIACT. Focus groups will be conducted on participants who drop out and complete the programme to understand their experience and journey.

Curriculum

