The LIACT training curriculum is designed by registered clinical psychologists with consultation from local ACT experts from the Association of Contextual and Behavioural Science (Hong Kong Chapter). There are 5 modules in the intensive training block including introduction, professional and ethics issues, application of ACT low-intensity intervention, troubleshooting and preparation for clinical placement. The LIACT protocol is also piloted and revised by clinical psychologists to ensure its adaptability to local situations. After 120 hours of intensive training, the training participants will attend a role-play exam to ensure their competency to proceed with the 9-month placement. During the 9-month placement, each PWP is expected to see at least 15 direct service beneficiaries to provide LIACT. During which, supervision will be provided regularly to ensure the quality of service delivery and risk management. There will be a mid-placement review and final placement review, and the training participants will submit audio recordings for supervisors to rate for their competence. Focus groups will be conducted for the training participants to understand their learning experience.

Treatment

Guided self-help LIACT will be provided to eligible participants. For individual guided self-help LIACT service, intake assessment will be conducted to assess the presenting problem of the participants at pre-treatment to ensure the suitability to receive LIACT service. Participants will be given the LIACT self-help workbook collaboratively with a PWP. Between each session, clients will read through the workbook and complete the exercises suggested in the workbook. In subsequent sessions, PWP will guide clients to overcome the difficulties in performing the LIACT exercises.

Therapists

PWPs will be responsible for providing LIACT to the participants. PWPs have completed a 120-hour intensive training and pass the role play examination prior to placement provision. The training was provided by experienced clinical psychologists and counsellors. Moreover, PWPs are under regular supervision by clinical psychologists, experienced counsellors, or social workers with extensive ACT training.

Outcome Measures

Training evaluation.

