6. Therapeutic alliance: The Working Alliance Inventory (WAI) was developed by Horvath and Greenberg in 1989. The brief revised version (Brief Revised Working Alliance Inventory; BR-WAI) consists of 12 items available multilingually (including Chinese). The scale is rated on a 5-point Likert scale, ranging from 1 (never) to 5 (always).
7. Experiential avoidance: The Brief Experiential Avoidance Questionnaire (BEAQ; Gámez et. al., 2014) is a shortened 15-item self-report measure designed to assess experiential avoidance, or the avoidance of uncomfortable or distressing thoughts and emotions. These statements are scored on a scale ranging from 1 (strongly agree) to 6 (strongly disagree).
8. Work Productivity and Activity Impairment: Work Productivity and Activity Impairment Questionnaire: General Health (WPAI) was developed by Reilly et. al. (1993) to measure impairments in both paid work and daily activities due to health-related problems. The domains covered include work time missed, impairment at work, productivity loss and activity impairment.

9.

Data analyses

For individual service, only the data of participants who have attended two or more follow-up sessions will be included for analysis. The first assessment session will not be counted for this requirement. Firstly, inter-correlations among all outcome measures will be assessed with Pearson's correlation coefficients. Secondly, the changes in outcome variables between pre-treatment, post-treatment and 3-month follow-up will be evaluated with repeated measures ANOVA. Cohen's *d* will be calculated to assess the relative effect sizes. Furthermore, reliable significant improvement will be computed according to the method recommended by Jacobson & Truax (1991), which is the division of pre-post treatment score difference by the standard error.

Compliance

The protocol of this study complies with the Declaration of Helsinki, IGH-GCP and research ethics principles to protect the rights, safety and well-being of participants.

References

doi:10.1111/j.1600-0047.2004.00329.x

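### The plan says it will evaluate the efficacy of LIACT, but a single-group pre-post study cannot attribute change to the treatment

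*Combined protocol and SAP*

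**What the plan says.** The service part is a within-person design: "Repeated measures design will be adopted for this study" (Research design). Everyone who qualifies is treated: "Guided self-help LIACT will be provided to eligible participants" (Treatment). The Data analyses section tests change across pre-treatment, post-treatment and follow-up by repeated measures ANOVA, with Cohen's d, and adds that "reliable significant improvement will be computed" by the Jacobson and Truax method. It mentions no control, waiting-list, benchmark or untreated comparison, and neither does any other section.

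The wording of what will be concluded varies:

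- Introduction (Mental Health in Hong Kong) gives the gap as: "the effectiveness of LIACT in a local context has yet been examined".
- Aims of the study names the effectiveness of the intervention as a focus, and then says: "The second part of the evaluation is to examine the outcomes of low-intensity psychological interventions, delivered by the trainees".
- Research design goes furthest: "Recovery rate and reliable improvement rate will also be used as indicators to evaluate the efficacy of LIACT".

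Natural recovery, regression to the mean and limits on causal interpretation are not mentioned.

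**The concern.** Efficacy is a causal claim: clients did better than they would have done without LIACT. A study in which every eligible person is treated does not observe that alternative. Participants are recruited because they have symptoms and are followed for three to four months, which is long enough for scores to move without treatment. A recovery rate, a reliable improvement rate or a significant ANOVA would count all of that movement as treatment success. If the plan is followed as written, the report could draw an efficacy conclusion that an inert service might also have produced.

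The plan also counts reliable change in one direction only. Without the share who reliably worsen, a reader cannot judge how much of the improvement rate random fluctuation alone could generate.

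**Working it through.** **No figure in the plan to reproduce.** The service target of 300 comes without alpha, power, effect size, SD or dropout. The documents give no reliability and no untreated change. The Data analyses section does not say which standard error the reliable-change index uses, and the recovery rate is not defined, so only the reliable improvement rate can be illustrated.

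**Assumptions, none from the documents.** PHQ-9 SD 5; reliability (rel) 0.80 or 0.89; correlation (r) between two untreated scores three to four months apart 0.5 or 0.7; untreated mean fall (drift) 0, 1 or 2 points; normally distributed change; 150 people analysed. The treatment effect is zero throughout.

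**Step 1, reliable-change cut.** Cut = 1.96 × SD × √(2(1 − rel)).

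- rel 0.80: 1.96 × 5 × √0.40 = 6.2 points
- rel 0.89: 1.96 × 5 × √0.22 = 4.6 points

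**Step 2, SD of untreated change.** SD of change = 5 × √(2(1 − r)), which is 5.00 at r = 0.5 and 3.87 at r = 0.7.

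**Step 3, share beyond the cut.** Improved = P(Z > (cut − drift) / SD of change). Worsened = P(Z < (−cut − drift) / SD of change).

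| rel | r | Drift 0: improved / worsened | Drift 2: improved / worsened |
|---|---|---|---|
| 0.80 | 0.7 | 5.5% / 5.5% | 13.9% / 1.7% |
| 0.80 | 0.5 | 10.8% / 10.8% | 20.1% / 5.1% |
| 0.89 | 0.7 | 11.8% / 11.8% | 25.1% / 4.4% |
| 0.89 | 0.5 | 17.9% / 17.9% | 30.2% / 9.4% |

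**Step 4, chance of a significant pre-post change.** Paired t-test, two-sided 0.05, n = 150, noncentrality = (drift / SD of change) × √150.

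- 1-point drift: (1/5.00) × 12.25 = 2.45, power 68%; (1/3.87) × 12.25 = 3.16, power 88%.
- 2-point drift: noncentrality 4.90 and 6.32, power above 99% in both.

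As a cross-check, the smallest paired standardised change detectable with 80% power is (1.96 + 0.84)/√n: 0.229 at n = 150 and 0.162 at n = 300. Small changes unrelated to treatment would be declared significant.

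**Step 5, regression to the mean on its own.** A separate simulation used true score plus error, no treatment effect and no natural recovery. It assumed PHQ-9 mean 8 to 12, SD 5 and reliability 0.60 to 0.85, and selected on the first reading below 20 (the plan's exclusion).

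- Assumed lower cut of 5 or 10, selecting score used as baseline: mean fall 0.03 to 2.06 points; reliable improvement 2.1% to 5.2%, against a nominal 2.5%.
- No lower cut: the mean rises by 0.01 to 0.23 points.
- A second, non-selecting reading used as baseline: mean change zero to within 0.01 in every scenario.

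Regression to the mean can therefore bias the mean change and Cohen's d, but it moves the reliable improvement rate little. For the rates named in the efficacy sentence, natural recovery and real fluctuation over months matter more.

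**The case against.** The best defence is context. This is a programme evaluation, the second part aims to examine outcomes, and the hypotheses predict change after the intervention. Read that way, the efficacy sentence is loose wording. That is fair as to intent, and the outcome-describing sentence in the Aims is one the design can support. But the plan nowhere limits the causal reading, so the efficacy sentence stands as its stated conclusion.

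A second objection is that the magnitudes rest on assumptions. This also stands. The 30% needs a 2-point drift together with the higher reliability and the lower correlation; without drift the range is 5.5% to 18%. The power figures are for a paired t-test, whereas the plan uses ANOVA over three time points. They show what is possible and predict nothing about this study. The causal point does not depend on them.

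Three stronger readings are tempting, and the documents do not support them:

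- **That the plan already holds two pre-treatment readings and ignores one.** A PHQ-9 is needed for the exclusion at 20 or more, the Exclusion criteria refer to "information emerging at triage assessment", and "Clinical outcomes (depression and anxiety levels) will be measured at every session". But triage, the intake assessment and the first assessment session may be one contact. No interval is given, a screening GAD-7 is only implied, and nothing names the triage score as the baseline.
- **That regression to the mean must inflate the results.** The criteria set no numeric lower cut, and excluding PHQ-9 of 20 or more pushes the mean the other way. Size and direction are both open.
- **That the share who worsen would match the share who improve by chance.** This holds only at zero drift. In the 30.2% scenario only 9.4% worsen, so deterioration gauges random fluctuation and cannot reveal natural recovery.

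**Conclusion.** Wrong as written. The plan claims to evaluate efficacy with a single-group pre-post study that has no comparator, benchmark or untreated period. That conclusion follows from the documents alone.

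Its size depends on the assumptions listed above. With no treatment effect, reliable improvement would be recorded in 5.5% to 18% of clients at zero drift and in up to 30% with a 2-point untreated fall. A 1-point fall would be significant in about 68% to 88% of studies with 150 analysed. Regression to the mean is a possible contributor of unknown sign.

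A reader might infer that the design itself is unacceptable or that a control arm is required. Neither follows: the study can describe change during the service, and the fault lies in the conclusion claimed for it.

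**What to change.** 1. In Aims of the study and Research design, replace efficacy and effectiveness with *pre-post change among people receiving LIACT*, and state that the change is not attributed to treatment.
2. In Data analyses, report the reliable deterioration rate beside the reliable improvement rate, with the same index and denominator. Present it as a gauge of random fluctuation, and say that it does not expose natural recovery.
3. State whether the screening or triage PHQ-9 (and GAD-7, if taken) is a separate contact from the pre-treatment reading. Only if it is, use the later, non-selecting reading as baseline and report the screening to pre-treatment change descriptively, with its interval. Note that the two-week recall windows may overlap, and that this change does not estimate natural recovery over three to four months.

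The cost is rewording, a little extra analysis of data already collected, and a less favourable headline.

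### The planned responder results count only recovery and reliable improvement, so reliable worsening is not separated from no change, and people with fewer than two follow-up sessions enter no quantitative outcome result.

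*Combined protocol and SAP*

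**What the plan says.** Research design names two responder indicators: "Recovery rate and reliable improvement rate will also be used as indicators to evaluate the efficacy of LIACT". Data analyses adds one responder calculation, reliable significant improvement by the Jacobson-Truax method, described as "which is the division of pre-post treatment score difference by the standard error". The other planned summaries of change are a repeated measures ANOVA and Cohen's d. No section names deterioration, worsening or any harm result.

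On who is analysed, Data analyses states that for the individual service "only the data of participants who have attended two or more follow-up sessions will be included for analysis", and adds: "The first assessment session will not be counted for this requirement".

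On data, Research design states: "Clinical outcomes (depression and anxiety levels) will be measured at every session". It also has the other outcome measures repeated after each session, as a guard against missing data from dropout.

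People who leave are covered in another way. Research design states: "Focus groups will be conducted on participants who drop out and complete the programme to understand their experience and journey". Aims of the study states: "Individual exit interviews and focus groups will be conducted". Curriculum provides for regular supervision covering service quality and risk.

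**The concern.** Both responder indicators look in one direction. Everyone who does not reliably improve falls into a single remainder, which mixes people who stayed the same with people who got reliably worse. The mean change and d include worsening but average it with improvement, so they do not say how many individuals worsened.

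The two-session rule adds to this. It removes people who stopped almost at once, and leaving early may be related to how someone was doing. Someone assessed, seen once more and then lost has a baseline and a later PHQ-9 and GAD-7, and the plan uses neither. The interviews, focus groups and supervision may bring such cases to light, but they give no rate.

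This is an uncontrolled evaluation of care delivered by trainees on placement. A reader deciding whether to extend the service will want to know how many people ended reliably worse. That number could be unfavourable, so it is best committed to before the data are seen.

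**Working it through.** The plan gives no figure to reproduce on this point. The checks below ask how large the unsplit remainder could be, whether the planned summaries already reveal worsening, and whether a deterioration rate would be precise enough to be useful.

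**1. Number of people.** Mental Health in Hong Kong says practitioners "will provide low-intensity acceptance and commitment therapy (LIACT) to around 300 adults". Service Participants gives 300 as the number for initial screening. The same background section plans 30 trainees, and Curriculum expects at least 15 clients each: 30 × 15 = 450. The analysed number is therefore an assumption; 300 is used below, with 150 and 450 as alternatives.

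**2. The unsplit remainder.** The introduction cites a programme with 63.7% reliable improvement. If LIACT matched it, 100% − 63.7% = 36.3% would not have reliably improved:

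- 0.363 × 150 = 54
- 0.363 × 300 = 109
- 0.363 × 450 = 163

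**3. Do the planned summaries fix the number who worsened?** The reliable-change threshold is 1.96 × SD × √(2(1 − r)). The plan gives neither SD nor r. Assumed values give:

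- SD 4, r 0.90: 1.96 × 4 × √0.20 = 3.5 points
- SD 6, r 0.80: 1.96 × 6 × √0.40 = 7.4 points

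Take two invented samples of 100, everyone starting at PHQ-9 = 17 (below the exclusion limit of 20). Entries are points of improvement.

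| | Sample A | Sample B |
|---|---|---|
| Changes | 25 at +8, 25 at +16, 25 at +3, 25 at −3 | 25 at +9, 25 at +15, 40 at +2, 10 at −8 |
| Sum; mean | 600; 6.0 | 600; 6.0 |
| Sum of squares | 8450 | 8450 |
| SD of change | √(84.5 − 36) = 6.96 | 6.96 |
| Paired d (mean ÷ SD of change) | 0.86 | 0.86 |
| Reliably improved, any threshold 3.5 to 7.4 | 50 | 50 |
| Post-treatment scores | 9, 1, 14, 20 | 8, 2, 15, 25 |
| Recovered, any cut-off from below 10 to below 14 | 50 | 50 |
| Reliably worse, any threshold 3.5 to 7.4 | **0** | **10** |

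The pre-post mean, SD of change, paired d, improvement rate and recovery rate all agree, yet the number reliably worse differs. The example is artificial. All start at one score, so a d scaled by baseline SD is undefined in both samples, and it covers pre to post only. It shows that the planned outputs need not reveal the count; it says nothing about how often people worsen.

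**4. An ordinary shape.** Suppose change is roughly normal. Take mean change 1.41 × 4 = 5.64 (the depression effect size from another cohort cited in the introduction, times an assumed baseline SD of 4), an assumed SD of change of 5 or 6, and a 4-point threshold. With whole-point scores, worsening by 4 or more means change below −3.5:

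- SD 5: Φ((−3.5 − 5.64)/5) = Φ(−1.83) = 3.4%
- SD 6: Φ((−3.5 − 5.64)/6) = Φ(−1.52) = 6.4%

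That is about 10 to 19 people of 300, on assumed inputs.

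**5. People outside the analysis set.** The documents give no early-leaving rate. Each 10% of starters with fewer than two follow-up sessions would be 30 of 300, or 45 of 450.

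**6. Would a rate be informative?** Exact binomial 95% intervals:

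| Reliably worse | Rate | 95% interval |
|---|---|---|
| 0 of 300 | 0% | up to 1.2% |
| 15 of 300 | 5.0% | 2.8% to 8.1% |
| 0 of 150 | 0% | up to 2.4% |
| 8 of 150 | 5.3% | 2.3% to 10.2% |

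At these numbers the rate is usable, and a low one would be real reassurance.

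**The case against.** The strongest reply is that nothing planned is wrong. No estimate is biased by the lack of a deterioration row, worsening does enter the mean and d, and for the planned set the count can be computed at any time from the same scores. Under an ordinary shape of change the planned summaries suggest a small share worse, as step 4 shows. All of this stands, and it limits the point to an advance commitment on reporting. It does not remove the point: step 4 depends on an assumed shape, whereas counting does not.

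The two-session rule also has a rationale. One recovery benchmark in the introduction is for participants with two or more sessions, so a similar set helps comparison. That is a reason to keep the planned set, not to make it the only one.

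Finally, a last-score analysis mixes people with very different numbers of sessions, and no cut-off or reliability value is stated that could simply be reused. Both are fair, and the fix allows for them.

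A reader might infer more than the documents support:

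- *That all dropouts are excluded.* Only those with fewer than two follow-up sessions are. Later dropouts remain in the stated set, though the plan does not say how the ANOVA would treat their missing values.
- *That many clients may be getting worse, or that LIACT causes it.* The documents give no deterioration rate, and without a control group no rate could be attributed to the intervention.
- *That worsening goes unwatched.* High-risk people are excluded at triage and supervision covers risk. What is absent is a reported count.
- *That referrals during LIACT should be counted as part of this point.* Onward referral is described only for people found ineligible, and escalation is part of the model. A count would need records the plan does not describe, so it is not asked for here.

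**Conclusion.** The point holds as a gap in reporting. The plan commits to recovery and reliable improvement but not to reliable deterioration, and its analysis rule discards later scores that it collects from people who leave after one follow-up session. No planned estimate of mean change is shown to be invalid.

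The true size is unknown, because the documents give neither a deterioration rate nor the share below the two-session threshold. The 109 of 300 without a planned split rests on the cited 63.7% and an assumed 300 analysed; the 3.4% to 6.4% rests on assumed normality, SDs and threshold. The change is worth making because it costs little, reduces the selection created by a stated rule, and lets a trainee-delivered service report both directions of change.

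**What to change.** In Data analyses:

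1. State the reliability value, the standard error and the cut-off for the Jacobson-Truax index in advance. Apply the same index and cut-off in both directions, and report improved, unchanged and reliably deteriorated on PHQ-9 and GAD-7.
2. Do this for the planned set, kept for comparability with the two-session benchmark, and also for everyone who starts LIACT and has at least one later session score, using the last available score.
3. State how many starters the two-session rule excludes and how many have no later score.
4. Describe the deterioration figure as an uncontrolled rate, not as an effect of LIACT.

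The cost is one extra table from scores already collected. The downsides are a last-score analysis that mixes different numbers of sessions, which the table should say, and a possibly less favourable picture. The planned ANOVA and Cohen's d are unchanged.
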